## LIST OF ABBREVIATIONS AND DEFINITION OF TERMS

ACE:	angiotensin-converting enzyme
ADA:	anti-drug antibody
AE:	adverse event
ALT:	alanine aminotransferase
AP:	alkaline phosphatase
APR:	acute phase reactions
ASMD:	acid sphingomyelinase deficiency
AST:	aspartate aminotransferase
ATC:	anatomic category
AUC 0-last :	area under the curve extrapolate from time 0 to the time corresponding to the last quantifiable concentration
AUC 0-τ :	area under the plasma concentration curve during a dosing interval $\tau$
BMB:	bone marrow burden
BMD:	bone marrow density
BMI:	body mass index
BQL:	below the quantification limit
CL:	clearance
C max :	maximum plasma concentration observed
CRS:	cytokine release syndrome
CSR:	clinical study report
CV:	coefficient of variation
DBP:	diastolic blood pressure
DBS:	dry blood spot
DL co :	diffusing capacity of lungs for carbon monoxide
DLT:	dose-limiting toxicity
DUP24:	Duplication 24
DXA:	dual-energy X-ray absorption
ECG:	electrocardiogram
eCRF:	electronic case report form
EQ-5D:	EuroQol –5 dimensions quality of life questionnaire
ETP:	extension treatment period
FACIT:	Functional Assessment of Chronic Illness Therapy
FEV 1 :	forced expiratory volume in the first 1 second
FVC:	forced vital capacity
GGT:	gamma glutamyl-transferase
Hb:	hemoglobin
HDL:	high-density lipoprotein
HLGT:	high-level group term
HLT:	high-level term
HR:	heart rate
HRCT:	high-resolution computed tomography

IAR:	infusion associated reactions
ICF:	informed consent form
ILD:	infiltrative lung disease
IMP:	investigational medicinal product
INR:	international normalized ratio
ISS:	integrated summary of safety
IXRS:	interactive voice/web response system
LDL:	low-density lipoprotein
LFT:	liver function test
LLOQ:	lower limit of quantification
LLT:	lower-level term
MAR:	missing-at-random
MedDRA:	Medical Dictionary for Regulatory Activities
mITT:	modified intent to treat
MMRM:	mixed model for repeated measures
MN:	multiples of normal
MRI:	magnetic resonance imaging
NMR:	nuclear magnetic resonance
NPB-HAQ:	Niemann-Pick B Health Assessment Questionnaire
PAP:	primary analysis period
PCSA:	potentially clinically significant abnormality
PFT:	pulmonary function test
PGIC:	Patient Global Impression of Change
PGIS:	Patient Global Impression of Symptom Severity
PKDM:	pharmacokinetics, dynamics and metabolism
PRO:	Patient reported outcome
PT:	preferred term
ROW:	rest of world
SAE:	serious adverse event
SAP:	statistical analysis plan
SBP:	systolic blood pressure
SD:	standard deviation
SEM:	standard error of the mean
SF-36:	Short Form-36 Health Survey
SMQs:	standard MedDRA queries
SOC:	system organ class
SRS:	splenomegaly-related score
TEAE:	treatment-emergent adverse event
TLC:	total lung capacity
ULN:	upper limit of normal
US:	United States
VLDL:	very low-density lipoprotein
V ss :	volume of distribution at steady state
WBC:	white blood cells
WHO-DD:	World Health Organization-Drug Dictionary
WMW:	Wilcoxon-Mann-Whitney

WT: Wildtype  
 $\beta$ -HCG:  $\beta$ -human chorionic gonadotropin

## 1 OVERVIEW AND INVESTIGATIONAL PLAN

This statistical analysis plan (SAP) focuses on descriptions of strategy and statistical methodology for the analysis of clinical data from DFI12712 trial. It has been developed based on DFI12712 Amended Clinical Trial Protocol 11 dated 05 August 2019. This version replaces the previous versions of the SAP.

A clinical study report (CSR) will be prepared when the 52-week primary analysis period (PAP) data become available. At study completion, ie, at the end of the extension treatment period (ETP), a CSR for the entire study including ETP will be prepared.

### 1.1 STUDY DESIGN AND RANDOMIZATION

This Phase 2/3, multicenter, repeat-dose, clinical trial will be divided into 2 consecutive major periods: 1) a randomized placebo-controlled, double-blind PAP from Day -60 to Week 52 to be followed by 2) an ETP. Initially, the ETP will be double-blind as patients in the placebo arm cross over to active treatment. Study drug will be defined during the PAP as olipudase alfa or placebo, and during the ETP as olipudase alfa, and will be administered intravenously once every 2 weeks for 52 weeks in PAP, then for ETP. Day -60 to -1 is part of screening period with no study drug; some of the screening assessments which are not repeated right before the first infusion of study drug on Day 1 serve as baseline value for the study.

After completing the PAP, patients will enter the ETP of the study. Those who were randomized to the active arm will continue receiving the dose they were receiving at the completion of the PAP. Patients randomized to the placebo arm in the PAP will cross over to active treatment in the first infusion in ETP and will undergo dose escalation to a target dose of 3.0 mg/kg olipudase alfa.

For treatment periods during the PAP and the ETP, dose-limiting toxicity (DLT) criteria (protocol Section 8.1.4) and study stopping rules (protocol Section 8.1.5) will apply. If a patient satisfies protocol-specified criteria of rescue therapy (protocol Section 8.1.6), the individual treatment blind will be broken and the patient if on placebo will be switched to olipudase alfa; for patients already on olipudase alfa, the treatment will continue unless the patient drops out of study.

### 1.2 OBJECTIVES

#### 1.2.1 Primary objectives

The primary objective of this Phase 2/3 study is to evaluate the efficacy of olipudase alfa (recombinant human acid sphingomyelinase) administered intravenously once every 2 weeks for 52 weeks in adult patients with acid sphingomyelinase deficiency (ASMD) by assessing changes in: 1) spleen volume as measured by abdominal magnetic resonance imaging (MRI) (and for the United States [US] only, in association with patient perception related to spleen volume as measured by splenomegaly-related score [SRS]); and, 2) infiltrative lung disease as measured by the pulmonary function test DLco.

### 1.2.2 Secondary objectives

- To confirm the safety of olipudase alfa administered intravenously once every 2 weeks for 52 weeks
- To characterize the effect of olipudase alfa on the patient perception related to spleen volume as measured by SRS after 52 weeks of study drug administration (For the United States, the effect of olipudase alfa on SRS is part of the primary objective)
- To characterize the effect of olipudase alfa on the following endpoints assessed sequentially:
  1. The effect of olipudase alfa on liver volume after 52 weeks of study drug administration
  2. The effect of olipudase alfa on platelet count after 52 weeks of study drug administration
  3. The effect of olipudase alfa after 52 weeks of study drug administration on fatigue
  4. The effect of olipudase alfa after 52 weeks of study drug administration on pain
  5. The effect of olipudase alfa after 52 weeks of study drug administration on dyspnea

### 1.2.3 Additional objectives

- To characterize the effect of olipudase alfa on liver function tests (LFT)
- To characterize the effect of olipudase alfa on infiltrative lung disease via pulmonary imaging
- To characterize the effect of olipudase alfa on pulmonary functioning
- To characterize the effect of olipudase alfa on the fasting lipid profile
- To characterize the effect of olipudase alfa on bone disease
- To characterize the effect of olipudase alfa on cardiopulmonary functioning
- To characterize the effect of olipudase alfa on biomarkers
- To characterize the effect of olipudase alfa on hematology parameters
- To characterize the effect of olipudase alfa on selected health-related quality of life questionnaires and questions therein
- To characterize the pharmacodynamic effect of olipudase alfa on clearing sphingomyelin accumulation in liver and/or blood
- To characterize the multiple-dose plasma pharmacokinetic profile of olipudase alfa
- To explore the effect of olipudase alfa on Physician's global assessment of change
- To explore the effect of olipudase alfa on the nuclear magnetic resonance (NMR) profile of high-density lipoprotein (HDL)
- To explore the effect of olipudase alfa on liver function via echo-Doppler ultrasound
- To explore the effect of olipudase alfa on inflammatory and vascular biomarkers

### 1.3 DETERMINATION OF SAMPLE SIZE

The sample size calculations are based on the 2 primary efficacy endpoints:

1. Percentage change in DLco (expressed as % predicted of normal) from baseline to Week 52
2. a) For Europe and the rest of the world (ROW) outside of USA: the percentage change in spleen volume (expressed in multiples of normal [MN] ) from baseline to Week 52  
  
b) For US: the combination spleen endpoint which consists of two components: the percentage change in spleen volume (expressed in MN) from baseline to Week 52 and change in splenomegaly-related score from baseline to Week 52.

Although the multiplicity adjustments in statistical testing of hypotheses ensures the study to be positive if only one of the two primary endpoints is significant ([Section 2.4.5.3](#)), each endpoint has been powered adequately in order to choose the sample size for the study as 36 randomized patients in 1:1 ratio in placebo and olipudase alfa treatment arms.

Endpoint	Null hypothesis	Assumptions			Signif. level	Sample Size N	Power
		Trt Diff	SD	Non-evaluable			
DLco	There is no difference between olipudase alfa group and placebo group in percentage change from baseline in percent predicted DLco from baseline to Week 52.	25%	20%	11%	0.05	36	0.93
Spleen Volume	There is no difference between olipudase alfa group and placebo group in percentage change from baseline in spleen volume in multiples of normal from baseline to Week 52.	30%	11.8%	11%	0.05	36	0.99
SRS	There is no difference between olipudase alfa group and placebo group in change from baseline in SRS from baseline to Week 52.	8	9.4	11%	0.15	36	0.82

The following assumptions for the DLco endpoint are based on results obtained from the olipudase alfa Phase 1b study DFI13412:

- A 20% common standard deviation
- A 25% mean difference from baseline to Week 52 between olipudase alfa and placebo in percentage change in DLco (in % predicted)
- An expected exclusion rate from the primary analysis due to non-availability of results at Week 52 is 11%

Based on these assumptions, a comparison between the olipudase alfa arm and the placebo arm will have 93% power using a t-test at a 2-sided 5% significance level and with 36 patients randomized 1:1 to placebo and olipudase alfa.

The assumptions for the spleen volume endpoint are the following:

- An 11.8% common standard deviation based on data from previous ASMD and Gaucher disease Type 1 studies
- A 30% mean difference from baseline to Week 52 between olipudase alfa and placebo in percentage change in spleen volume (MN)
- An expected exclusion rate from the primary analysis due to non-availability of results at Week 52 is 11%

Based on the above assumptions, a comparison between olipudase alfa and placebo will have over 99% power using a t-test at a 2-sided 5% significance level with 36 patients randomized 1:1 to placebo and olipudase alfa. At 2.5% significance level, the power will still be over 99%.

The assumptions for the splenomegaly-related score endpoint came from the Sanofi-sponsored clinical trial in myelofibrosis (JAKARTA, NCT# 01437787). The assumptions for the power calculations are the following:

- A common standard deviation of 9.4
- A mean difference of 8.0 from baseline to Week 52 between olipudase alfa and placebo in the SRS score
- An expected exclusion rate from the primary analysis due to non-availability of results at Week 52 is 11%

Based on the above assumptions, a comparison between olipudase alfa and placebo will have 82% power using a t-test to detect a statistical trend, defined as 2-sided p-value  $\leq 0.15$ , with 36 patients randomized 1:1 to placebo and olipudase alfa.

Using the simplifying assumption that the 2 components of the combination spleen endpoint are independent, the likelihood that statistical significance will be declared for the combination spleen endpoint is greater than 80%.

## 1.4 STUDY PLAN

This Phase 2/3, multicenter, repeat-dose, clinical trial will be divided into 2 consecutive major periods: 1) a randomized placebo-controlled, double-blind PAP from Day -60 to Week 52, to be followed by 2) ETP for up to 4 years. Initially, the ETP will be double-blind as patients in the placebo arm cross over to active treatment, and the last patient completes PAP and when this patient is going through dose escalation the study is unblinded for analysis of PAP; ETP after unblinding for PAP analysis is open-label where all patients receive olipudase alfa.

The PAP will include a screening/baseline period and a treatment period. Approximately 36 patients who meet the eligibility criteria will be randomized in a 1:1 ratio across sites into 1 of 2 arms, placebo or 3.0 mg/kg olipudase alfa target dose. Patients will undergo a dose-escalation period to achieve the target dose level.

After completing the PAP, patients will enter the ETP. Patients randomized to the placebo arm in the PAP will cross over to active treatment in the ETP and will undergo dose escalation to a target dose of 3.0 mg/kg olipudase alfa. The patients who were randomized to the active arm will continue receiving olipudase alfa at the dose they complete PAP (with a mock dose escalation period to maintain blinding).

Study drug will be administered intravenously once every 2 weeks. In-patient hospitalization is required during dose escalation period and specific visits. Other infusions are administered at the clinic.

All patients will have an end of study/early discontinuation visit within 2 weeks after the last infusion of study treatment. In addition, all patients will receive a follow-up phone call for safety approximately 30 to 37 days after the last infusion of study drug.

A rescue strategy for patients who experience significant clinical decline (specific guidelines in the protocol, Section 8.1.6) will be in place: these individual patients may be unblinded and if receiving placebo, will be switched to olipudase alfa with proper dose escalation to a target dose of 3.0 mg/kg. These patients will continue to be followed to the end of study.

## 1.5 MODIFICATIONS TO THE STATISTICAL SECTION OF THE PROTOCOL

This section summarizes discrepancies between the statistical analysis described in the amended DFI12712 protocol 11, dated 12 August 2019, and this SAP.

- The following language about the summary of immune response assessments in the protocol Section 11.5.5.4 will not be provided by the dose level of the infusion before or during the evaluation, since the infusion information will be included in the data listing.  
*The presence, absence, and titers of serum anti-olipudase alfa IgG antibodies and routine levels of acute phase reactants will be summarized over time overall and by the dose level of the infusion before or during the evaluation.*
- The following language about the exploratory pharmacodynamic analyses in the protocol Section 11.5.6.2 is not planned in this SAP but may be done ad hoc if deemed necessary.  
*Exploratory correlation analyses will be attempted to evaluate relationships between different PD markers and between sphingomyelin and /or lysosphingomyelin levels from different sources.*
- Multiplex assay of inflammatory and vascular biomarkers are analyzed as both exploratory efficacy and safety endpoints in the protocol but will be treated only as safety endpoints in this SAP.
- The ETP population mentioned in the protocol Section 11.4 was removed from the SAP, since data for PAP+ETP will be analyzed in a cumulative way.
- The annualized rate of TEAEs and separate analyses of AEs by demographic characteristics (eg, age and sex) mentioned in the protocol Section 11.5.5.1 will be presented in the integrated summary of safety and will not be done in the study SAP.

- Protocol Section 11.5.6.3 for pharmacokinetic-pharmacodynamic analyses will not be done at the study level, but may be conducted using pooled data from different clinical studies and the results may be included in a separate report.
- For the summary of exposure, the protocol mentioned using the safety population. However, the population was changed to mITT population in the SAP in order to accurately summarize the duration of exposure prior to rescue therapy for patients who were randomized to placebo at the beginning.

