11.5.5.1 Adverse events

Pretreatment AEs will be listed and presented separately from treatment-emergent AEs.

All AEs will be coded using the most recent version of the MedDRA. Adverse event incidence tables will present by system organ class (SOC) (sorted by internationally agreed order) and preferred term (PT), and the number and percentage of patients experiencing an AE. Multiple occurrences of the same event in the same patient will be counted only once in the tables within a treatment period. The denominator for computation of percentages is the safety population within each treatment arm.

All treatment-emergent adverse events (TEAEs), all TEAEs potentially related to study drug, all TEAEs leading to treatment discontinuation and/or study discontinuation, all TEAEs that are IARs, all TEAEs that are SAEs (including those potentially related to treatment), and all AEs with fatal outcome (including fatal TEAEs) will be summarized. The TEAE observation period will be defined as the time from the first infusion of study drug through the end of study visit or 30 to 37 days after the last infusion of study drug, whichever one occurs later.

Detailed listings of TEAEs, SAEs, AESIs, related AEs, and discontinuations due to AEs will be provided and include the randomized treatment arm and olipudase alfa dose of the infusion or placebo before or during the occurrence of the AE, when applicable.

The number of TEAEs and annualized rate, and the number and proportion of patients reporting specific AEs will be tabulated for the overall analyses of AEs.

Separate analyses of AEs may also be conducted by demographic characteristics (eg, age and sex). Adverse events of special interest, such as IARs, and SAEs will be analyzed similarly.

Adverse events of special interest

Detailed listings for AESIs will be provided.

Deaths

The following deaths summaries will be generated:

- Death in nonrandomized patients or randomized and not treated patients
- Treatment-emergent AE leading to death (death as an outcome on the AE CRF page as reported by the investigator) by primary SOC and PT

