#### **2.4.4.2 Compliance**

Compliance to the treatment regimen will be monitored in terms of the percentage of scheduled infusions the patient receives during the treatment periods, irrespective of whether the infusion was total or partial. This is calculated as:

$100 \times (\text{number of infusions received}) / (\text{number of infusions intended to be received})$

For PAP, the number of infusions intended to be received is 27 over 52 weeks for a patient who complete PAP.

Noncompliance in PAP is defined as missing 2 or more consecutive infusions in PAP (excluding for cause misses, such as when the missed doses are required by the protocol due to a DLT) or 4 or more infusions in total in the 52-week PAP treatment period.

Noncompliance in PAP+ETP is defined as missing 4 or more infusions in every 52-week period following PAP treatment period until the end of study.

Treatment compliance for overall PAP will be summarized descriptively as quantitative variable using mITT population and randomized treatment group.

The percentage of patients whose compliance is  $\leq 85\%$  (missing 4 or more infusions out of scheduled 27 infusions in PAP) will be provided. In addition, number and percentage of patients with noncompliance, and by reasons (missed 2 or more consecutive infusions not for cause (“not for cause” means there is no justifiable reasons for a missed dose, eg., DLT), or missed 4 or more infusions in total in the 52-week PAP) will be provided.

Similar summaries will be provided for PAP+ETP.

A case of overdose will be reported as an AE and will be summarized with AE. An overdose is defined in Section 10.4.1.3 of the protocol.

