##### **2.4.6.1 Adverse events**

Pre-treatment adverse events are defined as those that have an onset date/time before the first infusion date/time of the patient. Treatment emergent adverse events are those that have an onset date/time in the treatment epoch. Any AE reported in the database with onset date after the end of the treatment epoch will be classified as post-treatment.

The epochs for safety analysis have been defined in [Section 2.1.5](#). Treatment-emergent adverse events will be presented for different periods under different treatment groups as follows (and as appropriate):

1. Adverse events started in PAP treatment epoch, by randomized treatment group.
2. Adverse events started in either PAP or in ETP while taking olipudase alfa. This will be presented by randomized treatment group as well as combined (ie, all patients treated with olipudase alfa).

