### ***Generalities***

The primary focus of adverse event reporting will be on treatment-emergent adverse events. Pretreatment adverse events will be described separately.

If an adverse event date/time of onset (occurrence, worsening, or becoming serious) is incomplete, an imputation algorithm will be used to classify the adverse event as pretreatment, or treatment-emergent. The algorithm for imputing date/time of onset will be conservative and will classify an adverse event as treatment emergent unless there is definitive information to determine it is pretreatment. Details on classification of adverse events with missing or partial onset dates are provided in [Section 2.6.2](#). If an AE worsens in severity, two AEs of same verbatim but with different start/end dates and different severity are captured separately on the AE log page in the eCRF.

The AE log page in the eCRF captures the date when the event become serious. If and when this date is non-missing, it indicates that the AE started as non-serious and became serious at a later date. To account for non-serious and serious parts of the AE collected in one AE log page, this AE will be split into two AEs – one non-serious, and one serious AE – with the same AE number, with the following modifications in data for these two AEs:

- Non-serious AE: AE end date, AE outcome, date of death or hospitalization, autopsy information, criterion for serious adverse event (SAE) will be blank.
- Serious AE: AE start date will use the date the event became serious.

Action taken towards study drug and action taken toward AE will be considered in relation to the date the event became serious, the last infusion date and dosing information, and a determination will be made, in consultation with safety monitor of the trial, as to whether the recorded fields belong to non-serious AE or serious AE; then the decision will be implemented in analysis. Any such decision will be rationalized in the CSR.

The adverse events summary will be presented by SOC and PT sorted by the internationally agreed SOC order and decreasing frequency of PTs within SOCs within the olipudase alfa treatment arm, unless otherwise specified. Multiple occurrences of the same event in the same patient will be counted only once in the tables within a particular treatment phase. The denominator for computation of percentages is the safety population within each treatment group.

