#### **2.4.6.14 PAP+ETP safety analyses**

For categorical measures, such as AE, data throughout both PAP and ETP will be summarized as three groups:

- **Previous placebo group** includes patients who are randomized to placebo. For patients in this group, only the data during olipudase alfa exposure at ETP will be summarized. The baseline will be defined as the last non-missing value prior to first olipudase alfa infusion at ETP.
- **Previous olipudase alfa group** includes patients who are randomized to olipudase alfa. For patients in this group, all the data during PAP and ETP with olipudase alfa exposure will be summarized. The baseline will be defined as the last non-missing value prior to first olipudase alfa infusion at PAP.
- **Overall Olipudase alfa group** includes patients from previous placebo group and Previous Olipudase alfa group.

For continuous measures collected at longitudinal time point, such as labs and vital signs, data throughout both PAP and ETP will be summarized as two groups:

- **Placebo/olipudase alfa group** includes patients who are randomized to placebo. For patients in this group, all data during PAP and ETP will be summarized at each longitudinal time point. The baseline will be defined as the last non-missing value prior to first infusion of IMP at PAP.
- **Olipudase alfa/Olipudase alfa group** includes patients who are randomized to olipudase alfa. For patients in this group, all the data during PAP and ETP with olipudase alfa exposure will be summarized at each longitudinal time point. The baseline will be defined as the last non-missing value prior to first infusion of IMP at PAP.

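### The PAP+ETP adverse-event table compares and pools columns about one year apart in olipudase exposure, and the study report has no exposure-adjusted rate

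*SAP*

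**What the plan says.** SAP 2.4.6.14 defines three groups for categorical safety measures such as adverse events.

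- Previous placebo: "For patients in this group, only the data during olipudase alfa exposure at ETP will be summarized".
- Previous olipudase alfa: "For patients in this group, all the data during PAP and ETP with olipudase alfa exposure will be summarized".
- Overall: both groups combined.

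SAP 2.4.6.1 confirms the side-by-side and pooled display for events on olipudase alfa: "This will be presented by randomized treatment group as well as combined". The general rules in that section fix the percentage: "The denominator for computation of percentages is the safety population within each treatment group", and "Multiple occurrences of the same event in the same patient will be counted only once in the tables" within a treatment phase.

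Protocol 11.5.5.1 plans more than percentages: "The number of TEAEs and annualized rate, and the number and proportion of patients reporting specific AEs will be tabulated", for the overall analyses of adverse events. SAP 1.5 lists this as a departure from the protocol. The annualized rate, together with the analyses by demographic characteristics, "will be presented in the integrated summary of safety and will not be done in the study SAP". That bullet gives no reason, although several of its neighbours do.

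Cumulative olipudase exposure is still summarized (SAP 2.4.4.1), by randomized group in the mITT population (SAP 2.4.4).

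**The concern.** A patient followed longer on drug has more opportunity to record a first event. The two columns differ in time on drug by design, and the percentage has no time element. At the same underlying risk, the previous-olipudase column can therefore look worse. A reader could take that as harm building up with longer treatment. The pooled percentage mixes two exposure lengths and changes between reports as follow-up grows. This matters because SAP section 2 expects the PAP database to hold ETP data for most patients already, and allows a further report during the ETP.

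The exposure summary does not let a reader rebuild a rate. It uses the mITT population, while adverse events use the safety population. The adverse-event section does not specify event counts. The time windows also differ: exposure runs from the first olipudase infusion, whereas the previous-placebo column takes ETP data only. A placebo patient rescued during the PAP could contribute olipudase time without the events from that time. SAP 2.4.6.1, by contrast, counts events on olipudase alfa in either period.

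**Working it through.** **Exposure gap.** The SAP's own figure is that "the number of infusions intended to be received is 27 over 52 weeks" (SAP 2.4.4.2). Infusions every 2 weeks from Week 0 to Week 52 give 52/2 + 1 = 27, so it reproduces. Placebo patients receive their first olipudase infusion at Week 54 (Protocol 6.1). The scheduled gap is therefore 27 infusions, or 54 weeks; 52 weeks is the nominal PAP length.

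**Exposure ratio**, previous olipudase to previous placebo, with E years of ETP and a one-year gap: (E + 1)/E. This is 3.0 at E = 0.5, 2.0 at 1, 1.5 at 2 and 1.25 at 4. Protocol 6.2.1 sets the ETP at 2 to 4 years; shorter values of E apply at the PAP cut or an interim report.

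**Crude percentages under identical risk.** The documents give no event rates, so the rate λ is an assumption, shown over a range. With constant λ, P(at least one event) = 1 − exp(−λ × years), using E years for previous placebo and E + 1 for previous olipudase.

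| λ per year | E = 0.5 | E = 1 | E = 2 | E = 4 |
|---|---|---|---|---|
| 0.1 | 4.9 v 13.9% | 9.5 v 18.1% | 18.1 v 25.9% | 33.0 v 39.3% |
| 0.3 | 13.9 v 36.2% | 25.9 v 45.1% | 45.1 v 59.3% | 69.9 v 77.7% |
| 0.5 | 22.1 v 52.8% | 39.3 v 63.2% | 63.2 v 77.7% | 86.5 v 91.8% |
| 2.0 | 63.2 v 95.0% | 86.5 v 98.2% | 98.2 v 99.8% | 100 v 100% |

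Example at λ = 0.3, E = 1: 1 − exp(−0.3) = 25.9% and 1 − exp(−0.6) = 45.1%. A 54-week gap changes the λ = 0.3 row by less than 1 point. With equal column sizes, the pooled figure in that row is (13.9 + 36.2)/2 = 25% at E = 0.5, 36% at E = 1 and 74% at E = 4.

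**Front-loaded risk.** Assume 2 per year for the first 16 weeks on drug and 0.1 per year afterwards, with 52 ETP weeks and a 54-week gap.

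- Expected events, previous placebo (52 weeks): 2 × 16/52 + 0.1 × 36/52 = 0.685. Crude: 1 − exp(−0.685) = 49.6%. Annualized: 0.685/1 = 0.68.
- Expected events, previous olipudase (106 weeks): 2 × 16/52 + 0.1 × 90/52 = 0.788. Crude: 54.5%. Annualized: 0.788/(106/52) = 0.39.

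Here the crude gap is only 5 points, but the annualized rate differs by a factor of 0.68/0.39 = 1.7 in the other direction.

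**Equal window.** Counting only the first 52 weeks on olipudase gives 25.9% in both columns for λ = 0.3 and 49.6% in both for the front-loaded case. It is the only one of the three measures that is level under both risk patterns.

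**Precision.** With about 18 patients per arm, one patient is 5.6 points. At 25.9% v 45.1%, the standard error of the difference is √(0.259 × 0.741/18 + 0.451 × 0.549/18) = 16 points.

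**The case against.** The strongest reply has four parts.

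1. **The move is declared.** SAP 1.5 exists to list departures from the protocol, and it says where the rate will appear. A reader might infer that the SAP silently removes a promised analysis; the documents do not support that. What stands is narrower: the study report lacks the rate, and nothing in these documents commits the integrated summary to showing it for these three columns.
2. **The protocol promise is limited.** It covers the overall analyses of adverse events. Rates in every SOC/PT row, or by these columns, were never promised, because the columns are defined in the SAP. This is correct, and the fix stays within it.
3. **The constant rate may not fit.** Protocol section 4 describes first-dose-related toxicity in Phase 1, and the amendment history in Appendix C links infusion reactions and transaminase elevations to dose escalation. Both columns start at first olipudase infusion and both include true escalation, so for such events the crude gap is small. This also stands, and it means an annualized rate alone would not be neutral.
4. **The display is descriptive.** No systematic testing is planned (SAP 2.4.6), each column's data window is stated and exposure duration is tabulated. That lowers the risk of misreading without removing it, since readers compare descriptive percentages by eye.

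**Conclusion.** The concern holds as a reporting gap of low severity. The columns differ by about one year of olipudase exposure, the percentages ignore time at risk, and the study report has no exposure-adjusted adverse-event measure.

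For events arising at a constant rate, the spurious gap is largest at early cuts: 22 points after half a year of ETP and 19 points after one year at an assumed 0.3 per year. It falls to 8 points after four years. It is also small for escalation-related events, and for very common events at late cuts. These sizes rest on assumed rates and on equal follow-up within each column, neither of which the documents give.

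A reader might go further and conclude that the table will mislead. The documents support only that it can, depending on the data cut and on when events occur. The randomized PAP comparison has equal planned duration in both arms and is not affected.

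**What to change.** 1. In SAP 1.5, delete the annualized-rate part of the bullet. The part on demographic characteristics can stay.
2. In the PAP+ETP adverse-event overview table, report for each of the three columns the patient-years on olipudase alfa, number of TEAEs and TEAEs per patient-year beside n (%). Rates in every SOC/PT row are not needed.
3. Use one population and one olipudase window for both events and exposure. State in SAP 2.4.6.14 that a rescued placebo patient's PAP time on olipudase, and the events in it, are both included, so that it agrees with SAP 2.4.6.1 and 2.4.4.1.
4. Add one table of n (%) with TEAEs over equal time since first olipudase infusion, for example the first 52 weeks in both columns, with the number of patients who have reached the end of that window. This covers front-loaded risk, where the annualized rate alone makes the shorter-exposed column look worse.

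The cost is one additional table and a few extra rows, from data already collected.
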